8.0 Statistical Considerations

The figure below depicts the structural equation model (SEM) analysis of the data from this study (through Post) and the R33 study that will follow it (through Follow-up, f-u). We will conduct an inferential test of the critical a_2 path – representing the effect of intervention on our primary target variable, momentary negative affect (mNA) - from our SEM analysis. We conducted a power analysis using G*Power and with a post-treatment sample size of 102 and a medium effect size for the a_2 path (i.e., a .50 standard deviation post-treatment condition effect), alpha = .05 and a one-tailed test, we will have power of .81. Our initial sample size for the R61 was 126 (42 per site, 21 per condition per site) so that even with close to 20% attrition, we will still end up with 102 at post-treatment.

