## Data Analysis Plan

*Average momentary negative affect (mNA).* We created scalar invariant latent average mNA variables using the 7 EMA NA items (sad, tired, irritable, nervous, angry, afraid, and lonely) at pre- and post-intervention. Each item at each of the two time points represented the participant's average score on that item across all the EMA prompts at that time point. Unstandardized loadings were constrained to equal one for each item to create a latent, unweighted average variable and were so constrained across time; each item's intercept was constrained to be equal over time. Together, these constraints on the loadings and intercepts result in the latent average mNA variable being scalar invariant over time; that is, the latent variable has the same scale over time such that changes from pre to post can be interpreted quantitatively.

We included a priori correlated residuals for each item with itself from pre- to post-intervention. Standardized loadings were salient ( $\geq .30$ ) for each of the 7 items at both pre (average loading = .53; range = .34 to .81) and post (average loading = .50; range = .30 to .79). Thus, the latent average mNA variable was well defined at both T1 and T2. We then saved factor score estimates for each participant for their latent average mNA at pre and post for the analyses of whether the intervention impacted average mNA. The factor score determinacy coefficients equaled .89 at both pre and post. Testing for group differences on the average mNA factor score estimates at pre showed that the intervention and control condition did not differ significantly at T1 ( $t = .67$ ,  $df = 108$ ; 2-tailed  $p = .50$ ; Cohen's  $d = .20$ ).

*Stressor-independent negative affect.* The measure of stressor-independent mNA (mNA-SI) was derived from a similar scalar invariant latent variable model as for latent average mNA

---

All factor score determinacy coefficients reported are for participants with complete data on the measure's indicators.

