Momentary negative affect (mNA) in the presence of stressor(s) has been taken to reflect the individual's baseline levels of mNA, mNA-SI, and their change in mNA in reaction to stressors, mNA-SR (e.g., Bolger & Schilling, 1991; Shackman et al., 2016). Thus, the second step in deriving a mNA-SR measure at T1 and T2 was to partial the mNA-SI score from the latent mNA in the presence of a stressor at that time point. The residuals of these regressions represent the increase in NA in reaction to a stressor; we saved these scores to use as the mNA-SR measure. Testing for group differences in mNA-SR at pre showed that the intervention and control condition did not differ significantly at T1 ( $t = -.11$ ,  $df = 98$ ; 2-tailed  $p = .91$ ; Cohen's  $d = -.02$ ). Importantly, mNA-SR was less temporally stable from pre to post ( $r = .73$ ) than the almost perfectly stable mNA-SI ( $r = .96$ ), thus, indicating that there was more change in mNA-SR than mNA-SI over the course of the study. Indeed, mNA-SR was a little less temporally stable from pre to post than the estimate of the latent average mNA ( $r = .78$ ) indicating somewhat more change in mNA-SR than mNA over the course of the study.

*Effects of the mindfulness intervention on mNA, mNA-SI and mNA-SR.* Although still debated, there are some contexts in which difference scores are preferable to analyses of regressed change to estimate change over two time points (e.g., Maxwell & Delaney, 2004; Rogosa, 1995; Willet, 1988; [name] et al., 2010). There is consensus, however, that regressed change is preferable to difference scores in the context of a randomized design (e.g., Maxwell & Delaney, 2004; [name] et al., 2010). Thus, in the current randomized design, we used regressed change to test the effect of the mindfulness intervention on mNA-SI, mNA-SR, and mNA. That is, for each of these variables, we performed a regression in which the individual's post score was the dependent variable, the individual's pre score was a covariate, and intervention condition was the main predictor of interest.

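### Protocol 8.0 tests the primary target variable through an SEM path, but the SAP regresses saved factor scores by an unnamed method, which under regression-type scoring understates the size of the effect

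*SAP*

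**What the plan says.** Protocol 8.0 (Statistical Considerations) names the test: "We will conduct an inferential test of the critical a_2 path", which it describes as "representing the effect of intervention on our primary target variable, momentary negative affect (mNA) - from our SEM analysis". The same section says the model covers the present study through post-treatment and the R33 through follow-up.

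The SAP (Data Analysis Plan) uses latent models only to build the measures. For mNA it fits a two-wave model of seven items, with all unstandardized loadings fixed at one and item intercepts equal over time, so that change can be read on the item-average scale. It then says "We then saved factor score estimates for each participant for their latent average mNA at pre and post for the analyses of whether" the intervention had an effect. The test is a separate regression: the "post score was the dependent variable", the pre score is a covariate, and condition is the predictor of interest.

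The SAP argues for regressed change over difference scores. It gives no reason for regressing saved scores instead of estimating the path inside the SEM. It names no scoring method and does not say whether the two waves were scored together.

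**The concern.** A latent post variable regressed on latent pre and condition is also regressed change, so the SAP's argument does not explain the move away from 8.0. The two routes need not give the same number. Regression-type factor scores are pulled toward the mean. When they come from a joint two-wave model, post items also contribute to the pre score. The pre score then carries part of the treatment shift, and adjusting for it removes that part from the estimate.

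At stake is the reported size of the effect on the primary target variable. The unit loadings and equal intercepts were imposed to give the coefficient a direct quantitative reading, and regression-type scoring takes that away without any sign of it in the output. With the method unstated, a reader cannot tell which scale a reported coefficient is on.

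**Working it through.** **1. The plan's own figure.** Inputs from Protocol 8.0: "post-treatment sample size of 102" (51 per arm at 1:1), "a .50 standard deviation post-treatment condition effect", and "alpha = .05 and a one-tailed test, we will have power of .81". Noncentrality = 0.50 × √(51/2) = 2.525. The normal approximation gives Φ(2.525 − 1.645) = 0.811; the noncentral t with 100 df gives 0.806. The stated .81 reproduces. It is a plain two-group comparison with no measurement model and no baseline covariate.

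**2. Inputs for the estimator check.**
- From the SAP: standardized loadings at pre (mean .53, range .34 to .81) and post (mean .50, range .30 to .79), determinacy .89 at both waves, and pre-post correlation of estimated mNA .78, taken as the score correlation.
- Assumed: the individual loadings, for example .34, .40, .45, .50, .58, .63, .81 at pre and .30, .37, .42, .48, .54, .60, .79 at post, which match those means and ranges.
- Assumed: the residual correlation of each item with itself over time, 0 to .6. The SAP includes it but gives no size.
- True adjusted effect: 0.50 latent SD.

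**3. Each wave scored alone.** A regression-type score has expected value ρ² times the latent value, where ρ is the determinacy. With the SAP's .89: 0.50 × 0.89² = 0.50 × 0.792 = 0.396. With the matched loadings the result is 0.387. The score SD is ρ, so in score-SD units the effect is 0.50 × ρ: 0.50 × 0.89 = 0.445, or 0.44 with the matched loadings.

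**4. Both waves scored jointly.** The weights are W = ΦΛ′Σ⁻¹, where Φ is the latent correlation matrix, Λ the loadings and Σ the implied item correlation matrix. The coefficient for condition is (shift in post score) − b × (shift in pre score), where b is the slope of post score on pre score. The latent correlation was set so that the score correlation is .78. At residual correlation .3: 0.347 − 0.77 × 0.049 = 0.31. A simulation at N = 102 (4,000 replicates) gave a mean of 0.312.

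| Residual correlation | Coefficient, latent SD | In score-SD units |
|---|---|---|
| 0 | 0.29 | 0.32 |
| .3 | 0.31 | 0.35 |
| .5 | 0.33 | 0.38 |
| .6 | 0.35 | 0.40 |

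If .78 were the latent correlation instead, the coefficient would be 0.28 at residual correlation .3 and 0.31 at .5.

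**5. Bartlett scores.** The coefficient is 0.50 in latent SD. Divided by the larger SD of the Bartlett scores, it is about 0.44.

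**6. Which scoring do the SAP's figures suggest?** For stressor-independent mNA the SAP reports a pre-post correlation of .96 and determinacies of .82 and .86. Joint regression scoring with loadings matched to that model gives a correlation of .957 and determinacies of .81 and .86. Bartlett or wave-by-wave scores reach only about .85, even at a latent correlation of 1 and a residual correlation of .6.

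**7. The test itself.** Simulated one-sided type I error was 0.050. At residual correlation .3, power at N = 102 was 0.877 with joint regression scores and 0.880 with Bartlett scores.

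**The case against.** The figure that defines the SEM in 8.0 is not in the text available here. If mNA enters it as an observed score, regressed on its pre score and condition, the path coefficient equals the SAP's regression coefficient, and the mismatch is one of wording. The power calculation, a simple two-group comparison, does not settle this. That stands as a limit on how firmly the two documents can be called contradictory. It does not remove the shrinkage, which arises wherever regression-type scores are used.

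The SAP names no scoring method, so the shrinkage is conditional. This is largely answered by the stressor-independent figures, which fit joint regression scoring and are hard to reach otherwise. It remains an inference.

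The SAP is written in the past tense and reports two-group results, and the power text in 8.0 is for the two-condition R61. A reader might infer that having both estimators on file lets the sponsor choose after seeing results. The documents do not show this: the SAP already describes one analysis that was carried out.

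A reader might also infer that the two-step test is invalid or loses power, since it treats the scores as error-free. The simulation shows neither for mNA. Nor is there support for claiming distorted indirect effects: the SAP describes no such analysis and none was computed.

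**Conclusion.** The point holds as a problem of effect size. Protocol 8.0 places the test in an SEM; the SAP uses a two-step regression on scores of unstated type. Under regression-type scoring, a true 0.50 latent SD effect is reported as about 0.39 (wave by wave) or 0.29 to 0.35 (joint). In score-SD units this is about 0.44 to 0.45 or 0.32 to 0.40. The joint range rests on a score correlation near .78, loadings matched only in mean and range, and an assumed residual correlation of 0 to .6.

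Two tempting readings go too far. These figures are not the size of bias in any result the trial has reported; they show what the method does to an assumed effect of 0.50. Bartlett scores do not restore 0.50 as a Cohen's d: they restore the unstandardized coefficient, while the standardized one stays near 0.44. The change should be made, but the validity of the significance test is not in question.

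**What to change.** Preferred: add condition to the two-wave measurement model that the SAP already fits, regress latent post mNA on latent pre mNA and condition, and report that path as the primary estimate, in line with 8.0. For the three-arm R33, enter condition as two contrasts. Keep the factor-score regression as a sensitivity analysis, and state its scoring method and whether the waves are scored jointly.

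Alternative: amend 8.0 to the two-step method, specify Bartlett scores, and report the unstandardized coefficient in the item-average metric.

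The cost is one model statement in the SAP, or one sentence in each document. The downside of the preferred route is that the one-step model may need simplifying if it does not converge; the SAP should say in advance how that would be done.
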